We have previously demonstrated that the intake of macronutrients including glucose, cream and a high fat high carbohydrate (HFHC) fast food meal induces oxidative stress as reflected in an increase in ROS generation and an increase in plasma TBARS concentration(1). Furthermore, there is an increase in intranuclear NF κ B binding and a decrease in I κ B α , with an increase in IKK α and IKK β (2). Clearly, therefore, these macronutrients induce post prandial oxidative stress and inflammation. These observations have potential implications in terms of the relationships between macronutrient intake and atherogenesis since post prandial glycemia and lipemia have been implicated in this process. In this respect, it is also important that the oxidative stress and inflammation induced by a HFHC meal is of a greater magnitude and lasts for longer in the obese than in normal subjects(2). In addition, our work has also shown that the obese start with a higher level of basal (fasting) oxidative and inflammatory stress than normal subjects. Since T2D patients have higher basal levels of oxidative and inflammatory stress, it is likely they will respond to macronutrient challenge with greater levels of oxidative and inflammatory stress. In this respect it is also relevant that equicaloric meals composed of fruit and fiber do not induce oxidative and inflammatory stress(3).

Our experiments with cream have shown that its intake induces not only an increase in ROS generation but also lipid peroxidation products in plasma (TBARS). Our recent data show that cream intake induces an increase in NF κ B binding, IKK α and IKK β activity (Figure 1) and an increase in the expression of several pro-inflammatory cytokines including IL-1 β , IL-12 and IL-18 (Figure 2). It also induces an increase in another pro-inflammatory transcription factor, Egr-1, and c-fos (Figure 3). c-fos is a component of the transcription factor, AP-1 which regulates the expression of matrix metallo-proteinases (MMPs). Indeed, MMP-9 increases after cream intake and a HFHC meal (2). The pro-inflammatory effect of cream lasts for more than 3h.

[figure not shown]

Figure 1: Percent change in NF κ B (A) and IKK β (B) activities in MNC following cream intake. N=12, * $P<0.05$ by One Way Repeated Measures ANOVA followed by Holm-Sidak method for comparison versus the baseline, # $P<0.05$ by Two Way Repeated Measures ANOVA for comparison versus control group.

[figure not shown]

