During our experiments with cream exploring its effects on oxidative and inflammatory stress, we asked whether its intake would increase intracellular lipid in MNC. Indeed, we were able to demonstrate an increase in intracellular lipid in MNC both chemically and microscopically (**Figure 5-6**). These dramatic changes raised important issues. Firstly, it was important to define whether this increase was in monocytes, the cells which infiltrate the arterial intima to form foam cells by taking up lipid, and thus forming the fatty streak. The second was to define the type of lipid contained in these cells. We also asked whether these cells expressed more CD68, the characteristic marker for macrophages and whether they expressed more of PECAM, the adhesion molecule which is cardinal to the process of trans-endothelial transfer of leucocytes. Indeed, there was an increase in the expression of CD36, CD68 and PECAM. These findings were indicative of an increase in the ability of these cells to take up lipid, to transform to the macrophage phenotype and to develop the key adhesion molecule which would potentially facilitate their trans-endothelial transfer of these cells into arterial wall.

[figure not shown]

Figure 5: Lipid droplet accumulation in MNC after cream intake in normal subjects. Nile Red stain of MNC is shown before (0 hour) and after (1, 2 and 3 hours) lipid intake. At the indicated times, cells were fixed and stained for lipid. This experiment was performed 6 times. Peak lipid accumulation was at 2h. Results from one experiment are shown.

[figure not shown]

Figure 6: Intracellular accumulation of lipids in the MNC analyzed by Thin Layer Chromatography (TLC): A representative TLC of lipids extracted from the MNC at the baseline and following cream challenge in one of the subjects. Lane 1 is the pooled control sample, lane 2 represents intracellular lipids at the baseline and lanes 3, 4 and 5 represent intracellular lipids at 1, 2 and 3 hours following the cream intake.

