Visit 1 at week 0: Subjects will arrive after having fasted (10 hour) overnight. A fasting blood sample will be taken, followed by cream challenge and blood sample will be drawn 1, 2, 3 and 5 hours after the cream challenge. **Cream challenge:** Subjects will be given 100 mL of dairy cream (gourmet heavy whipping cream, Land 'O' Lakes Inc., Arden Hills, MN) to be consumed over 10 minutes. This preparation of dairy cream has 33 g fat (300 Calories) per 100 mL.

Subjects will then be given a supply of their drug to be taken once a day at bedtime.

Visit 2 at week 3: Subject will come fasting for a short visit for a blood draw at 4 weeks.

Visit 3 at Week 6: A fasting blood sample will be taken, followed by cream challenge same as the 1st visit and blood sample will be drawn at 1, 2, 3 and 5 hours after the challenge. Subjects will then be discharged from the study.

COMPENSATION FOR PARTICIPATION:

To help defray the costs of your participation, you will receive \$150.00 for completing the entire study. In the event that you do not complete the entire study, you will receive \$60.00 at Visit 1 and Visit 3 each, and \$30 for Visit 2. You will not be paid for the screening visit. . Please be aware that occasionally additional visits are

required, for safety evaluations or to repeat blood test, and that these visits are not a part of the 3 required visits. There will be no additional compensation for extra visits.

METHODS:

- 1) **MNC and PMN isolation by Ficoll-hyque method:** Blood samples will be collected in Na-EDTA as an anticoagulant. Three and a half mL of anticoagulated blood sample are carefully layered over 3.5 mL of PMN medium (Cedarlane Laboratories, Hornby, ON). Samples are centrifuged and at the end of the centrifugation, two bands separate out at the top of the RBC pellet. The top band consists of MNC, while the bottom consists of PMN. The MNC band is harvested and washed twice with Hank's balanced salt solution (HBSS). This method provides yields greater than 95% pure PMN and MNC suspensions.
- 2) **Monocytes isolation by magnetic beads.** Monocytes will be isolated from MNC fraction by magnetic beads coated with CD14 antibodies (Maltyni Biotec, Auburn, CA) .

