Statistical analysis will be carried out using SPSS and SigmaStat software (Jandel Scientific, CA). All data will be expressed as mean \pm S.E of arbitrary units and percent change is calculated from the means. To evaluate similarity between the study groups, baseline values for subject's demographics will be compared using appropriate parametric and non-parametric tests based upon the nature of the data. To account for the anticipated wide inter-patient variability, baseline measures will be standardized to 100%. All subsequent values will be reported as the percent change from the baseline value. Comparisons for each endpoint will be made using repeated measures ANOVA.

The primary endpoint of the study is to evaluate the change in intracellular lipids in MNCs following cream challenge before and after Vytorin therapy for 6 weeks. Our preliminary studies have shown an increase of 70 \pm 24% in intracellular lipids staining following cream intake in normal subjects. Assuming approximately a 25% decrease in the cream induced intracellular lipid accumulation, a sample size of 20 subjects per group should provide adequate power ($\beta = 0.8$) to detect a statistically significant difference ($\alpha = 0.05$), provided the standard deviation of the residuals is not equal to or greater than the mean difference.

Secondary endpoints: We will measure markers of monocyte activation including CD68 and PECAM expression as well as the activity and the expression of pro-inflammatory transcription factor NF- κ B and its activating protein, IKK β , the expression of pro-inflammatory NF- κ B-regulated genes, TLR-4, and SOCS-3 and oxidative stress in monocytes following cream challenge before and after Vytorin (simvastatin and ezetimibe). The decrease in intracellular lipids before and after combination of the Simvastatin and Ezetimibe will also be analyzed.

Data Safety Monitoring Plan:

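### The baseline behind the percent change and the scale of the primary lipid comparison are undefined, and no week-0 lipid covariate is stated; a same-visit baseline with an absolute target would put a post-treatment value in the week-6 denominator

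*Combined protocol and SAP*

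**What the plan says.** All references are to the combined protocol and SAP.

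- **Scale.** Section 9) DATA ANALYSIS gives wide variability between patients as its reason for standardising, and then states: "baseline measures will be standardized to 100%. All subsequent values will be reported as the percent change from the baseline value". The same paragraph also promises means and standard errors in arbitrary units.
- **Test.** "Comparisons for each endpoint will be made using repeated measures ANOVA". No factors, contrast or covariates are listed. The only baseline comparison described is of demographics.
- **Endpoint and planning figure.** The primary endpoint is the change in intracellular lipid after cream, before and after six weeks of Vytorin. Planning uses a rise of 70 ± 24% "in intracellular lipids staining following cream intake in normal subjects" and a decrease of about 25% in that rise.
- **Samples.** STUDY PROCEDURES has a fasting sample and samples at 1, 2, 3 and 5 h after cream at week 0, before the drug is supplied. The same is repeated at week 6: "A fasting blood sample will be taken, followed by cream challenge same as the 1st visit".
- **Secondary analysis.** "The decrease in intracellular lipids before and after combination of the Simvastatin and Ezetimibe will also be analyzed". Its scale and method are not given.
- **Hypothesis 1** (SPECIFIC AIMS) is that Vytorin reduces lipid accumulation in circulating monocytes. It does not say whether accumulation is absolute or relative to the fasting level.

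**The concern.** Two fasting samples could serve as the baseline, and the plan does not choose between them. In the preliminary work the word means the sample before a single cream challenge, as in the Figure 6 legend: "A representative TLC of lipids extracted from the MNC at the baseline and following cream challenge in one of the subjects". Carried over to this trial, that usage divides each visit's rise by the same visit's fasting value. At week 6 that value has been taken after six weeks of randomised treatment and may itself respond to the drug.

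If the question is how much lipid the cells take up in absolute terms, a drug that lowers both the fasting level and the rise could show a reduced effect on the percent scale, none at all, or one of the wrong sign. If baseline means week-0 fasting, the denominator is safe. However, a week-6 post-cream level compared with it, without subtracting week-6 fasting, would mix a fasting shift with the cream response. Either way, the primary result could depend on a definition chosen after the data are seen.

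The lack of a stated week-0 covariate is a related matter. Adjusting for the week-0 response deals with variability between patients, which is the plan's own reason for standardising, and does so without a post-treatment denominator.

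**Working it through.** **The plan's own figure.** The only computed figure nearby is 20 per group for 80% power. With a 17.5-point difference, 24 taken as the SD and two-sided 0.05, n = 2(1.96 + 0.84)² × (24/17.5)² ≈ 29.5, so 30 per group. The stated 20 is not reproduced on these inputs. This point does not depend on it.

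**Inputs.** From section 9: a rise of 70% and a 25% decrease, read as relative, so 70 × 0.75 = 52.5. From Randomization: 10 per arm (section 9 says 20 per group; that conflict is a separate matter). Assumed, because the documents give no value: the fractional fall *f* in fasting lipid on Vytorin (negative for a rise), stable fasting lipid on placebo, and the between-visit correlation *r*.

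**Step 1: same-visit denominator, absolute target.** Set week-0 fasting to 100. Placebo rises by 70, which is 70%. Vytorin rises by 52.5 from 100(1 − f), which is 52.5/(1 − f) percent.

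| Fasting change on Vytorin | Vytorin, % rise | Difference from placebo, points |
|---|---|---|
| +10% | 47.7 | -22.3 |
| 0 | 52.5 | -17.5 |
| -10% | 58.3 | -11.7 |
| -20% | 65.6 | -4.4 |
| -25% | 70.0 | 0.0 |
| -30% | 75.0 | +5.0 |

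For a cut *c* in the rise, the difference is 70[(1 − c)/(1 − f) − 1]. It is zero when f = c and changes sign beyond that. If the 25% were meant as 25 points, then c = 25/70 = 0.357 and the effect would vanish at a fasting fall of 35.7%. The absolute increment differs by -17.5 in every row because the example fixes it there.

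**Step 2: week-0 denominator.** With week-6 fasting subtracted, the rise is 52.5/100 = 52.5% for every f. Without subtraction it is [100(1 − f) + 52.5 − 100]/100, or 52.5 − 100f percent. At f = 0.25 that is 27.5%, and the difference from placebo is -42.5 points instead of -17.5.

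**Step 3: what a week-0 covariate gains.** With one summary per visit, the group-by-visit contrast of a repeated measures ANOVA is a comparison of change scores. Assume equal variances σ² at both visits.

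- Change score: variance proportional to 2σ²(1 − r), with 18 df and t = 2.101.
- ANCOVA with one covariate, N = 20: variance proportional to σ²(1 − r²) × [1 + 1/(20 − 4)] = 1.0625σ²(1 − r²), with 17 df and t = 2.110.
- Variance ratio: 1.0625(1 + r)/2. Interval-width ratio: its square root × 2.110/2.101.

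| r (assumed) | Variance ratio | Interval-width ratio |
|---|---|---|
| 0.3 | 0.691 | 0.83 |
| 0.5 | 0.797 | 0.90 |
| 0.7 | 0.903 | 0.95 |
| 0.9 | 1.009 | 1.01 |

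On variance alone the two methods break even at r = 2/1.0625 − 1 = 0.88. With the t values included, the break-even is about 0.87.

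**The case against.** The defence is substantial, and most of it stands.

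- **The denominator is an inference.** The plan speaks of one baseline value, in the singular, and elsewhere uses the word for entry demographics and screening bloods. The figure legends that favour the same-visit reading (for example "followed by Holm-Sidak method for comparison versus the baseline" in Figure 1) come from single-challenge experiments, where only one baseline was possible. A reader might infer that the plan prescribes a post-treatment denominator. It does not say so; that is one of two readings.
- **A relative target is well supported.** The planning effect and most of the preliminary figures are percentages. If the relative rise is the target, equal proportional falls in fasting lipid and in the rise should give zero, and the same-visit percentage is the right quantity.
- **No fasting change is documented.** Complete masking needs a fall as large as the cut in the rise. A fasting rise would exaggerate the effect.
- **A shift would be visible.** The arbitrary-unit summaries and the secondary before/after lipid analysis would show it. The text also says values will be reported as percent change, not that percentages enter the ANOVA. This reduces the risk, but it does not settle which scale carries the primary test.
- **Week 0 is already used.** A before/after repeated measures comparison has week 0 as its within-subject comparator. A reader might infer that week-0 data are ignored; only covariate adjustment is missing.
- **The absolute scale is not plainly better.** METHODS item 6 scores cells from 0 to 4. A fasting mean above 4/1.70 = 2.35 cannot rise by 70%, so an absolute increment may also depend on the fasting level.

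**Conclusion.** The point holds as a gap in definition with a conditional consequence. Baseline and the primary scale are unspecified, and no week-0 lipid covariate is stated.

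Distortion on the same-visit reading needs three things together: a same-visit denominator, an absolute target and a treatment effect on fasting monocyte lipid. Given all three, the planned 17.5-point reduction shrinks to 11.7 at a 10% fasting fall, disappears at 25% and reverses beyond that. On the week-0 reading, the problem arises only if week-6 fasting is not subtracted.

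A reader might go further and conclude that the planned analysis is biased or will hide a drug effect. The documents do not support that, because they establish none of the three conditions. Nor do they support declaring the absolute scale correct.

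The case for ANCOVA does not depend on which scale is chosen. It narrows the interval relative to change scores unless the between-visit correlation is about 0.87 or higher, and then the loss is about 1% at r = 0.9. This should be fixed before unblinding. Confidence is medium, because the fasting change and the correlation are both assumed.

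**What to change.** Before unblinding, write into section 9:

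1. **Baseline**: which fasting sample is meant, week 0 or same visit.
2. **Primary scale**: absolute or relative cream-induced rise. This is the sponsor's choice.
3. **One post-cream summary**: for example the 2 h score (Figure 5 legend, normal subjects: "Peak lipid accumulation was at 2h") or the mean of 1, 2, 3 and 5 h, which could dilute a 2 h peak.
4. **Primary comparison**: arms at week 6 by ANCOVA, adjusting for the same quantity at week 0. For an absolute target, use the increment in score units (post-cream minus same-visit fasting). For a relative target, use the log ratio of post-cream to same-visit fasting, with a stated rule for samples whose mean score is 0.
5. **Reporting**: fasting score by arm as a separate result, and percent change as a descriptive display with its denominator named. If the absolute scale is chosen, check for scores near the ceiling of 4.

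**Cost.** This is SAP wording and a little more analysis; every sample needed is already scheduled. The covariate takes one error degree of freedom (18 to 17) and about 6% in variance at 10 per arm. Comparison with the group's earlier percent-change figures becomes less direct, though the descriptive display keeps it possible.

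### The analysis plan never names Vytorin versus placebo as the primary test: the endpoint is worded only as before and after Vytorin, and the repeated measures ANOVA has no stated arm factor or tested term

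*Combined protocol and SAP*

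**What the plan says.** All of the planned analysis is in section 9, Data Analysis, of the combined protocol and SAP.

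- Primary endpoint: "The primary endpoint of the study is to evaluate the change in intracellular lipids in MNCs following cream challenge before and after Vytorin therapy".
- Method: "Comparisons for each endpoint will be made using repeated measures ANOVA". No factors, interaction or tested term are given.
- Secondary endpoints: a list ending in "oxidative stress in monocytes following cream challenge before and after Vytorin".
- Added lipid analysis: "The decrease in intracellular lipids before and after combination of the Simvastatin and Ezetimibe will also be analyzed".
- The only comparison between groups that is spelled out: "To evaluate similarity between the study groups, baseline values for subject's demographics will be compared".
- Scale: "baseline measures will be standardized to 100" (per cent), with later values reported as percent change from baseline.
- Size: "a sample size of 20 subjects per group should provide adequate power", "provided the standard deviation of the residuals is not equal to or greater than the mean difference".

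The word placebo does not occur in this section. Elsewhere, the Subject Assignment and Randomization sections set up two arms of 10, Vytorin and matching placebo. Aims 1.1, 2.1 and 3.1 mention both treatments, Aim 2.2 mentions only Vytorin, and Aim 1.2 refers back to the drugs already mentioned.

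**The concern.** In a randomised, placebo-controlled trial the evidence for a drug effect is the difference between arms. A plan that words its primary endpoint as before and after the active drug, and leaves the ANOVA terms open, allows success to be declared on the Vytorin arm alone. Anything that moves both arms between week 0 and week 6, such as a second exposure to the challenge, an assay batch or a change in diet, would then count as drug effect, and the benefit of randomising would be lost.

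The open choice also has a pull in one direction. At the same number of subjects per arm, the within-arm test is the less valid test and the more powerful one. If the term is not fixed before unblinding, it can be chosen after the data are seen.

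**Working it through.** **1. Where a between-arm test could be stated**

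- Study Sample, Subject Assignment, Randomization: blinding, two arms, 10 in each. These describe the design and name no test.
- Aims 1.1, 2.1, 3.1: measurements before and after either treatment. Two separate within-arm tests would satisfy this wording as well as a between-arm test would.
- Aim 2.2: Vytorin only. Aim 1.2: ambiguous.
- Data Analysis: before and after Vytorin for the primary endpoint, the secondary endpoints and the added lipid analysis; groups compared only on baseline demographics.

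No section states the between-arm contrast on the endpoint.

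**2. The plan's own sample size**

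Inputs from Data Analysis: 20 per group, power 0.8 (printed as a value of β), α = 0.05, SD below the mean difference. Sidedness is not given; I assume two-sided. I take the limit, SD equal to the difference Δ, read first as the SD of the change, so d = Δ/SD = 1.

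- Normal approximation, two arms: n = 2(1.960 + 0.842)²/d² = 15.7, so 16 per arm. Noncentral t gives 17.
- 20 is therefore not reproduced as the minimum, but at 20 per arm power is 87%. Under this reading the plan's claim holds at 20 per group.

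**3. Power at the number randomised**

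With one value per visit, the arm-by-visit term is the two-sample t-test on the change: noncentrality d√(n/2), df = 2n − 2. The within-Vytorin test is a paired t-test: noncentrality d√n, df = n − 1. If the SD is instead the within-subject residual SD, the SD of the change is √2 times larger and d = 1/√2 = 0.707.

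| SD equal to Δ, read as | Between arms, 10 per arm | Between arms, 20 per arm | Within Vytorin, n = 10 |
|---|---|---|---|
| SD of the change (d = 1) | noncentrality 2.236: 56% | 3.162: 87% | 3.162: 80% |
| Within-subject residual SD (d = 0.707) | 1.581: 32% | 2.236: 59% | 2.236: 51% |

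The plan requires the SD to be smaller than the difference, so each figure is a lower bound for its SD reading.

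**4. What a within-arm test does with a common shift**

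Assume no drug effect, n = 10 and a shift c in both arms, in SD-of-change units. The within-Vytorin test has noncentrality c√10:

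- c = 0.25: 0.791, significant in 11% of trials
- c = 0.5: 1.581, significant in 29%
- c = 0.75: 2.372, significant in 56%

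Between arms the shift cancels (c − c = 0) and the rate stays at 5%. In 200,000 simulated trials at c = 0.5, the between-arm test was significant in 5.0%.

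**5. Details that the contrast still needs**

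- Samples are drawn at 1, 2, 3 and 5 hours, and how they enter the test is not said.
- The value set to 100% could be the week-0 fasting value or each visit's own. If fasting and post-cream lipid fell in proportion, the first would show a decrease and the second none.
- The primary endpoint names MNCs; Hypothesis 1 and the Nile Red scoring use monocytes.

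**The case against.** The strongest reply is that the intended comparison is obvious. The trial is randomised, double-blind and placebo-controlled. Aim 1.1, under the primary objective, covers both treatments. The sample size is given per group to detect a difference. The legends of Figures 1 to 4 show that this team uses a two-way repeated measures ANOVA against a control group. The closing sentence on lipids before and after the combination would largely repeat the primary endpoint if that were only a within-Vytorin change.

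This stands as evidence of intent. A reader might infer that the sponsor means to ignore the placebo arm, and the documents do not support that. But intent does not name a test. The same legends also report a one-way ANOVA against baseline, they describe preliminary data, and Data Analysis does not say which form is planned.

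Other points on that side also stand:

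- A repeated measures ANOVA can keep the four hourly samples as levels of a time factor, so a single summary is not required. Only the tested term must be named.
- In the background figures baseline is the pre-cream sample, which favours each visit's own fasting value, but the plan does not say so.
- The shift sizes in the illustration are assumed. They show the mechanism and do not estimate this trial's error rate. A shift towards more lipid would not be read as a drug benefit.
- It is tempting to say that naming the contrast lowers power from 80% to 56%. It does not: under the SD-of-change reading the between-arm test has 87% at 20 per arm, so the shortfall comes from randomising 10 rather than 20 per group. Only under the residual-SD reading does 20 per group fall short as well.

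**Conclusion.** The concern holds as a failure to specify the primary test, and it must be fixed. The stated endpoint can be satisfied without using the placebo arm, and nothing in the plan fixes the ANOVA term that would bring that arm in. This rests on the text alone and I hold it with high confidence.

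The size of the consequence is conditional. The 29% against 5% contrast assumes a common shift of 0.5 SD of the change, two-sided 0.05 and 10 subjects per arm. The power figures assume an SD equal to the difference and, for the residual-SD reading, one value per visit. The conflict between 20 and 10 per group is a separate fault, which matters here because power has to be restated for whichever contrast is named. The time points, 100% reference and cell type are secondary details to settle when the term is written.

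**What to change.** Before unblinding, restate the primary endpoint along these lines: the Vytorin-minus-placebo difference in the week-0 to week-6 change in the cream-induced intracellular lipid response, tested on subject-level values by the arm-by-visit term of the repeated measures ANOVA, two-sided 0.05. An equivalent baseline-adjusted between-arm contrast at week 6 would serve equally well. Use the same contrast for the secondary endpoints and keep within-arm changes descriptive.

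In the same text, say:

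- how the 1, 2, 3 and 5 hour samples enter the test, as levels of a time factor or as one summary;
- which fasting value is set to 100%;
- which cell type is primary.

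Separately, reconcile 20 per group in Data Analysis with 10 per group in Randomization, say which SD the variability condition means, and restate the between-arm power at the number actually randomised.

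Naming the contrast is a wording change and adds no enrolment, visits or assays. The price is a less favourable stated power if 10 per arm is kept: at the limit of the plan's condition, 56% (SD of the change) or 32% (within-subject residual SD).

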Figure. 2: Percent change in plasma/Serum levels of various mediators: Graphical representation of values obtained by ELISA for IL-18 (A), ICAM-1 (B), PAI-1 (C) and MMP-9 (D). All values are presented as mean \pm SE. * $P<0.05$ by One Way Repeated Measures ANOVA followed by Holm-Sidak method for comparison versus the baseline, + $P<0.05$ by Two Way Repeated Measures ANOVA followed by Holm-Sidak method for comparison versus control group.

[figure not shown]

Figure 3 Percent change in mRNA levels of Egr-1 and c-fos by RT-PCR: All values are presented as mean \pm SE. n=12. * P<0.05 by One Way Repeated Measures ANOVA followed by Holm-Sidak method for comparison versus the baseline, + P<0.05 by Two Way Repeated Measures ANOVA followed by Holm-Sidak method for comparison versus control group.

In our most recent experiments, we have also shown that following the intake of cream the expression of TLR-4 (**Figure 4A**) is increased both at mRNA and protein level. This increase is observed at 1h and is sustained for at least 3h. Similarly, there is an increase in the expression of SOCS-3 following cream intake both at mRNA and protein levels (**Figure 1B**). This combination of effects is important since it has implications not only in terms of post prandial inflammation but also for a potential role in the pathogenesis of insulin resistance. The selective deletion of each of these two proteins leads to a protection from diet induced obesity related insulin resistance.

[figure not shown]

Figure 4: Percent change in mRNA levels of TLR4 and SOCS-3 by RT-PCR: All values are presented as mean \pm SE. n=12. * P<0.05 by One Way Repeated Measures ANOVA followed by Holm-Sidak method for comparison versus the baseline, # P<0.05 by Two Way Repeated Measures ANOVA followed by Holm-Sidak method for comparison versus control group.

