Randomization:

Subjects will be randomized to 2 groups with 10 patients in each using a computer generated randomization chart.

Group 1 will be getting vytorin 40/10 mg daily for 6 weeks

Group 2 will receive placebo daily for 6 weeks.

Inclusion Criteria for all groups:

- Age: 18 to 65 years of age.
- Obese (BMI \geq 30 kg/m²)
- LDL cholesterol of \geq 100 mg/dl
- Subject will be available for duration of the study and willing to comply with all study requirements
- Written and informed consent signed and dated
- Not taking any vitamins or antioxidants

Exclusion Criteria:

- Currently using anti-hyperlipidemic therapies
- Triglycerides >500 mg/dl.
- Myocardial infarction, angioplasty/stent placement or coronary artery bypass surgery in the past 6 months
- Patient on chronic use of non-steroidal anti-inflammatory drugs or steroids
- Hepatic disease
- Renal impairment
- History of drug or alcohol abuse
- Participation in any other concurrent clinical trial
- Use of an investigational agent or therapeutic regimen within 30 days of study.
- Smoker
- Pregnancy
- Premenopausal women who are not on birth control pills and have not had a hysterectomy or tubal ligation
- Anemia with hemoglobin <12 g/dl

RECRUITMENT OF SUBJECTS:

The recruitment into the study will be carried out by the following methods:

1. Patients for the Diabetes-Endocrinology Center of WNY Clinic
2. Diabetes-Endocrinology Center of WNY - Research Division - Recruitment Database

Accrual Rate: On an average, we plan to recruit 1 patient per week.

All subjects will have completed the following procedures prior to participating in the study.

1) Medical History;

2) Physical Exam

3) Informed consent

4) Baseline lab draws to measure CBC, SMA and lipid profile. All labs will be drawn in the fasting state in the morning before 10am.

Informed Consent

Study process and required visits will be explained to patient in lay terms. All subjects will be asked to sign a consent form approved by IRB and a copy given to all subjects.

STUDY PROCEDURES

Subjects will be randomized to receive Vytorin or matching placebo for 6 weeks.

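### The 80% power statement is not supported by the plan's own figures and does not apply to the 10 per group that the trial randomises

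*Combined protocol and SAP*

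**What the plan says.** METHODS, item 9 (DATA ANALYSIS) gives the only sample-size justification, and it concerns the primary endpoint. It reports a pilot rise of 70 ± 24% "in intracellular lipids staining following cream intake in normal subjects" and assumes a reduction of about 25% in that rise. It then states that "a sample size of 20 subjects per group" gives adequate power at α = 0.05, "provided the standard deviation of the residuals is not equal to or greater than the mean difference". Power is written as β = 0.8.

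The same paragraph sets a reporting convention, "All data will be expressed as mean" ± S.E., and the legends of Figures 2 to 4 use it too ("All values are presented as mean" ± SE). Neither statement is tied to the 70 ± 24%.

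The design sections give a different size. Study Sample plans 20 volunteers in all, and Randomization says "Subjects will be randomized to 2 groups with 10 patients in each".

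**The concern.** A power statement that carries a condition is only as good as the evidence that the condition holds. Here the only spread on offer is 24. Taken at face value it is larger than a quarter of 70, and if it is an SE the underlying SD is larger again. The group size in the statement is also twice the one in the randomisation.

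At stake is how a null result on the primary endpoint would be read. If 80% power is believed, a null result looks like evidence that Vytorin does not reduce lipid loading after cream. If the true power is well below that, a null result says little.

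**Working it through.** **Inputs.** From METHODS, item 9: rise 70, spread 24, reduction 25%, α 0.05 (two-sided assumed, as the plan does not say), 20 per group. From Randomization: 10 per group. Pilot n is not stated for the 70 ± 24%. For the SE reading I assume the sizes shown elsewhere in Background: 6 (Figure 5, lipid staining of MNC), 8 (Figure 7, monocytes) and 12 (Figures 1, 3 and 4, other assays).

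**Method.** Two-sample t-test between groups, standardised effect d = difference/SD, noncentrality d × √(n/2), 2n − 2 degrees of freedom. Points are percentage points of baseline.

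**1. The plan's own figure.** At the limit of its condition, SD = difference, so d = 1. Then 80% power needs 17 per group, and 20 per group gives 87%. The figure of 20 at exactly 80% is not reproduced, but as a conditional statement it is true at 20 per group. At 10 per group the same d = 1 gives 56%. To reach 80% requires d = 0.909 at 20 per group and d = 1.325 at 10. The SD may therefore be up to 1/0.909 = 1.10 times the difference at 20 per group, but only 1/1.325 = 0.75 times at 10. This step uses no pilot SD.

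**2. Size of the assumed effect.** Relative reading: 0.25 × 70 = 17.5 points. Absolute reading: 25 points.

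**3. The pilot spread as stand-in for the residual SD.** SD reading: 24. SE reading: 24 × √6 = 58.8, 24 × √8 = 67.9, 24 × √12 = 83.1.

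| Difference | SD | d | Condition met? | Power, 20 per group | Power, 10 per group |
|---|---|---|---|---|---|
| 17.5 | 24 | 0.729 | no | 61% | 34% |
| 17.5 | 58.8 to 83.1 | 0.298 to 0.210 | no | 15% to 10% | 10% to 7% |
| 25 | 24 | 1.042 | yes | 89% | 60% |
| 25 | 58.8 to 83.1 | 0.425 to 0.301 | no | 26% to 15% | 15% to 10% |

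**4. Sensitivity to within-subject correlation r.** For a change between visits, SD of change = 24 × √(2(1 − r)), taking 24 as the SD of the rise at each visit. The rows for SD 24 in step 3 correspond to r = 0.5. All values of r here are assumptions.

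| r | SD of change | Power for 17.5 points, 20 / 10 per group | Power for 25 points, 10 per group |
|---|---|---|---|
| 0.3 | 28.4 | 48% / 26% | 46% |
| 0.5 | 24.0 | 61% / 34% | 60% |
| 0.7 | 18.6 | 83% / 51% | 81% |
| 0.8 | 15.2 | 94% / 68% | 94% |
| 0.9 | 10.7 | over 99% / 93% | over 99% |

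**5. Detectable difference at 10 per group, 80% power.** 1.325 × SD. With an analysed SD of 24 this is 31.8 points, or 31.8/70 = 45% of the rise. With the SD of change at r = 0.3, 0.7, 0.8 and 0.9 it is 37.6, 24.6, 20.1 and 14.2 points. On the SE reading at r = 0.5 it is 78 to 110 points, more than the whole rise.

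**The case against.** A reader might infer that the plan's condition fails however the pilot figure is read, and that 80% power has been disproved. The documents do not support that, for three reasons.

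- The plan does not say whether the 25% is relative or in points. Relative is the natural reading, since the plan applies the reduction to the rise itself. But at 25 points with 24 as an SD, 24 < 25: the condition holds and power at 20 per group is 89%.
- The condition concerns the residual SD of a repeated measures ANOVA. The 24 is the spread of a single-challenge rise in normal subjects. The residual SD in treated obese subjects is not given and could be smaller. At r = 0.8 the SD of change is 15.2, below 17.5. Failure is therefore unsupported by evidence to the contrary, not proven.
- Missing the condition is not the same as missing 80%. At 20 per group the SD can reach 17.5/0.909 = 19.3 before power drops below 80%, although 24 is above that too.

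A reader might also infer that no reading reaches 80% at 10 per group. That holds for a between-group test with the analysed SD equal to the pilot spread. It does not hold at higher correlations (81% for 25 points at r = 0.7; 93% for 17.5 points at r = 0.9), nor for a paired before-after test within one arm (83% for 25 points with n = 10 and an SD of differences of 24). The primary endpoint is indeed worded as before and after therapy, but a within-arm test makes no use of the placebo group.

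Finally, a reader might take 24 to be an SE and conclude that the trial could rarely detect its target. The convention leans that way, but the sentence in METHODS is a rule for the trial's own data, the lipid figures (5 to 7) carry no such label, and none of the assumed pilot sizes is linked to 70 ± 24%. The size of 12 comes from other assays.

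What survives all of this is that the plan offers no figure showing its condition to be met, and that its statement is for twice the randomised group size.

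**Conclusion.** The concern stands in a limited form: the stated power is unsupported, and it is not the power of the trial as randomised. The firmest part needs no pilot figure. Granting the plan its condition at the limit, power falls from 87% at 20 per group to 56% at 10, so the condition as written cannot secure 80% for 10 per group.

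The pilot-based sizes depend on assumptions that the plan leaves open. With a relative 25%, 24 as an SD and a correlation of 0.5, power is 61% at 20 per group and 34% at 10. With 25 points it is 89% and 60%. The SE-based figures (7% to 26% across both group sizes and both differences) also need an assumed pilot n and should be read as illustration only. Under this change-score model with 24 as an SD, 80% at 10 per group needs a correlation of about 0.85 for 17.5 points or about 0.69 for 25 points. The documents give no value to set against these.

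**What to change.** Rewrite the sample-size sentence in METHODS, item 9, so that it:

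- gives the power or the detectable difference for the 10 per group in Randomization (about 32 points between groups at 80% power if the analysed SD is 24, with a range over stated correlations such as that in step 5);
- says whether 24 is an SD or an SE, and gives the pilot n;
- says whether the 25% is relative or in percentage points;
- states the residual SD or within-subject correlation assumed, and either justifies the condition on the residual SD with it or removes the condition;
- writes power = 0.8 (β = 0.2) in place of β = 0.8.

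The cost is a stated power that will probably look less favourable. No extra patients are needed.
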